10.4.6 Unblinded Subjects

If a subject has become unblinded due to meeting Section 10.4.5 worsening criteria but has not been revised or has been unblinded for any other reason, they should continue to be followed through the two-year endpoint for ITT analysis. All study procedures will continue to be completed. A Protocol Deviation Form will be required for any subject who has become unblinded, unless they have undergone the cross-over procedure or an additional intervention per protocol.

10.4.7 Postoperative Injections

Subjects should not receive cortisone injections before the 3 month follow-up visit and should not receive hyaluronic acid (HA) injections prior to the 6 month visit. Injections should not be given within 2 weeks prior to a postoperative visit and when given, should be done after completion of subject reported outcome forms. Subjects receiving postoperative knee injections will continue to be followed per the study protocol.

10.4.8 Missed Follow-up Visits

Investigators are to ensure that all follow-up visits are completed and are done within the window indicated in **Table 1**. If a visit is missed or occurs outside of the window, a Protocol Deviation Form is to be completed.

In the event of difficulty in scheduling a subject, at least three attempts of follow-up contact should be completed at each follow-up visit. Should the subject continue to be unresponsive at the 2 year follow-up visit, at least two telephone contacts should be attempted and documented and a certified letter mailed, prior to

considering the subject lost to follow-up. Once loss to follow-up is definitively established, a Study Exit Form is to be completed to properly withdraw the subject from the study.

10.4.9 Unscheduled Office Visits

Investigators may see the subjects, at their professional discretion, outside of the visits described in the study protocol. If an adverse event (AE) is reported during an unscheduled visit, the AE should be documented in the same manner as for a study visit, per Section 11.0 Safety Management—Medical Events/Adverse Events. No additional data collection or Case Report Forms are required at the unscheduled visit.

10.5 Protocol Deviations and Violations

10.5.1 Investigators acknowledge that they are not permitted to deviate from this Protocol, except in emergency circumstances.

Under emergency circumstances, deviations from the protocol to protect the rights, safety and well-being of human subjects may proceed without prior approval of the Sponsor or reviewing IRB/REB. Such deviations will be recorded and reported to the Sponsor and reviewing IRB/REB as soon as possible.

All protocol deviations and violations shall include a corrective and preventive action plan to assist in the limiting of deviations from the Protocol in the future.

10.5.2 All protocol deviations (i.e. any change, divergence or departure from the procedures or protocol) shall be recorded with an explanation for the deviation on the Protocol Deviation Form. A simple protocol deviation does not impact the subjects' rights, safety, or well-being, or the completeness, accuracy or reliability of the study data. Deviations shall be reported by the Investigator to Zimmer Biomet within 30 days. Zimmer Biomet will analyze the information and assess the significance. Deviations must also be reported to the reviewing IRB/REB per policy.

Any deviations to inclusion or exclusion criteria must be submitted to Zimmer Biomet in writing, per section 10.5.4 and the reviewing IRB/REB, where applicable, for analysis and approval prior to subject enrollment.

10.5.3 All protocol violations (i.e. any deviation from the protocol that may impact the subjects' rights, safety, or well-being, or the completeness, accuracy or reliability of the study data, or a deviation from FDA or IRB/REB regulations or standards) shall be reported to Zimmer Biomet within 24 hours and to the reviewing IRB/REB per policy. A Protocol Deviation Form shall be completed that includes a full explanation of the event and outcome.

The Investigator will assist Zimmer Biomet in corresponding with the reviewing IRB/REB, where appropriate, to determine the appropriate course of action.

10.5.4 Protocol waivers/exceptions may be granted by the Sponsor on a case by

case basis as per request from sites. A description and rationale for the exception request should be put in writing on a Protocol Waiver/Exception Request Form. A Site Investigator will be required to sign off on the form, as well as a Sponsor Approver, prior to the enrollment of a subject or known deviation from the protocol. Should a deviation or violation be performed without prior written approval from all parties, the Investigator may be terminated from the study. Any deviation or violation from the protocol should be captured on a Protocol Deviation Form.

10.6 Withdrawal and Study Re-Entry

Subjects may withdraw or be withdrawn at any time during the course of the study, per subject request or at the discretion of the investigator. Investigators may withdraw a subject due to non-compliance with the protocol or follow-up visit schedule, occurrence of adverse events, death, or other reasons per their professional opinion. The date and reason for subject withdrawal is to be documented on the **Study Exit Form**.

If a subject is withdrawn or terminated due to medical safety considerations because of an adverse event, the adverse event must be followed by medical attention until the investigator determines the event is chronic or clinically stable and all study data related to the event recorded.

When a subject withdraws or is withdrawn, all study procedures completed and data collected prior to the date of withdrawal will be submitted to the Sponsor and included in the study database, unless the subject requests otherwise in writing.

Should a subject who previously chose to withdraw or were considered lost-to-follow-up wish to re-enter the study, a new Informed Consent will be required. The site may resume scheduled follow-up visits according to their follow-up schedule.

Since the pre-determined sample size includes an additional 27 patients to account for lost-to follow-up, subjects that are withdrawn from the study will not be replaced.

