9.4 Randomization Procedures

The surgeon will be blinded to the treatment group until the time of surgery to avoid potential selection bias during the screening process. The subject will be blinded to the treatment group throughout the study. The research coordinator will input the subject's Inclusion/Exclusion criteria into the Electronic Data Capture System, once all criteria has been confirmed, and select that the subject is ready to randomize when appropriate. Subjects may be randomized prior to surgery to allow for OR set-up. However, randomization should be performed as close to the time of surgery as possible to reduce the risk of randomization failures due to cancelled procedures.

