14.2 Hypotheses

The primary hypotheses to be tested are symbolically represented as:

$$H_0: CCS(S+A) \leq CCS(AA) \text{ VS } H_a: CCS(S+A) > CCS(AA)$$

Where CCS(S+A) and CCS(AA) are equal to the probabilities of achieving composite clinical success for subjects undergoing Subchondroplasty with arthroscopy (S+A) compared to arthroscopy alone (AA). First, superiority will be statistically tested at 12 months using $\alpha=0.01$. If $p \leq 0.01$, then it will be concluded that S+A is superior to AA in terms of the primary endpoint and the conditional hypothesis of superiority in terms of ADL improvements will be tested, also at $\alpha=0.01$. If $p > 0.01$ at month 12, the same

hypothesis will be tested at month 24 using $\alpha=0.04$, thereby controlling the overall study type 1 error rate to no more than 0.05 according to the Bonferroni inequality. If $p \leq 0.04$ at month 24, it will be concluded that S+A is superior to AA in terms of the primary endpoint and the conditional hypothesis of superiority in terms of ADL improvements will then be tested at $\alpha=0.04$. The superiority hypotheses involving CCS will be tested using one-sided normal approximation tests. The conditional superiority test for improvements in ADL will be tested using one-sided contrasts derived from a mixed model for repeated measures (MMRM) for change in KOOS ADL among subjects free from SSSI.

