14.5 Sample Size Determination

For testing the primary superiority hypothesis as defined above and assuming true CCS rates of 0.80 and 0.60 for S+A and AA, respectively, a total of 174 subjects (116 and 58, respectively) are need for 80% power. This value is increased by 15% to 201 to account for losses-to-follow-up (134 S+A and 67 AA).

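### Section 10.6 lets an investigator who knows the arm end follow-up for missed visits, non-compliance, adverse events or other reasons, without requiring month-12 and month-24 outcomes afterwards, so CCS outcomes can be lost for outcome-related reasons.

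*Combined protocol and SAP*

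**What the plan says.** Section 10.6 (Withdrawal and Study Re-Entry) allows withdrawal at the subject's request or at the investigator's discretion: "Investigators may withdraw a subject due to non-compliance with the protocol or follow-up visit schedule, occurrence of adverse events, death, or other reasons", the last of these resting on professional opinion. The date and reason go on the Study Exit Form. An adverse event behind a safety withdrawal must be followed until it is chronic or stable. Withdrawn subjects are not replaced. The section does not require KOOS Pain or SSSI status at months 12 or 24 after an investigator's withdrawal.

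Section 9.4: "The surgeon will be blinded to the treatment group until the time of surgery". The subject stays blinded throughout. After surgery, follow-up is by telephone or ePRO only (9.7, 9.7.1).

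Other sections lean towards keeping subjects:
- 10.4.8 makes a missed visit a protocol deviation, asks for at least three contact attempts per visit, and leaves the declaration of loss until late: "Should the subject continue to be unresponsive at the 2 year follow-up visit, at least two telephone contacts should be attempted", followed by a certified letter.
- 10.4.3 follows revised subjects to two years for ITT. Sections 10.4.4, 10.4.6 and 10.4.7 keep crossed-over, unblinded and injected subjects in follow-up.

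Section 14.8 makes mITT the primary population. Section 14.9 handles non-evaluable mITT subjects with a tipping-point grid and adds multiple imputation when more than 10% of data are missing.

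**The concern.** In a drug trial, withdrawal for an adverse event may stop exposure. Here the randomized intervention is over when the subject leaves the operating room, so withdrawal by the investigator mainly stops the telephone and ePRO contacts that supply the primary endpoint.

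The permitted grounds also overlap with that endpoint. CCS failure means an SSSI or less than 10 points of KOOS Pain improvement (14.1). Knee pain is a listed arthroscopic risk (5.7.2), every reoperation goes on an Adverse Event Form (10.4.3), and an adverse event leading to reoperation or revision is an SAE (9.7.2). A subject withdrawn for such an event, or for poor adherence, is plausibly more likely than average to be a CCS failure. Withdrawal before month 12 or 24 can turn that likely failure into a missing value. Because the decision-maker knows the arm, the loss could also differ by arm.

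The boundary with 10.4.8 is unclear as well. A subject who misses the month-3 and month-6 calls may be pursued to month 24 at one site and withdrawn at another, with both sites following the protocol.

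**Working it through.** **Inputs.** Section 14.5: CCS 0.80 (S+A) against 0.60 (AA), 174 evaluable (116 + 58), 80% power, enlarged to 201 (134 + 67). Section 14.2: α = 0.01 at month 12 and 0.04 at month 24; "The superiority hypotheses involving CCS will be tested using one-sided normal approximation tests". Assumed, not in the documents: true or observed success near 0.60 in both arms, and the loss patterns below. The number actually enrolled is not given, so planned sizes are used.

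**Step 1. The plan's own size.** Take one-sided α = 0.04, 2:1 allocation, and pooled rate (0.60 + 2 × 0.80)/3 = 0.7333.
- Uncorrected AA size: n = [1.7507·√(1.5 × 0.7333 × 0.2667) + 0.8416·√(0.60 × 0.40 + 0.80 × 0.20/2)]² / 0.20² = 50.7.
- With continuity correction: (n/4)·[1 + √(1 + 2 × 3/(2 × n × 0.20))]² = 57.97, so 58 AA and 116 S+A, total 174. This matches, although the correction is inferred.
- 174 × 1.15 = 200.1, rounded up to 201. Loss allowance: 201 − 174 = 27, of which 134 − 116 = 18 are S+A.

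**Step 2. Shift in observed CCS.** Assume 80 of 134 S+A subjects would succeed and that k S+A failures, and no one else, are lost. Observed rate = 80/(134 − k).

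| k | Observed CCS | Gain (points) | Missing of 134 | Missing of 201 |
|---|---|---|---|---|
| 0 | 80/134 = 59.7% | 0 | 0 | 0 |
| 4 | 80/130 = 61.5% | 1.8 | 3.0% | 2.0% |
| 6 | 80/128 = 62.5% | 2.8 | 4.5% | 3.0% |
| 10 | 80/124 = 64.5% | 4.8 | 7.5% | 5.0% |

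Each row is below the 10% imputation trigger on either denominator. The shift can run the other way: with 40 of 67 AA successes, losing 4 AA failures gives 40/63 = 63.5%, a gain of 3.8 points for AA.

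**Step 3. Effect on one data set.** Set S+A from Step 2 against AA at 40/67 = 59.7%, using z = difference / √[p̄(1 − p̄)(1/n₁ + 1/n₀)].
- k = 4: 0.0184/0.0734 = 0.25, p = 0.40.
- k = 6: 0.0280/0.0734 = 0.38, p = 0.35.
- k = 10: 0.0481/0.0733 = 0.66, p = 0.26.

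None approaches 0.04 or 0.01.

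**Step 4. Effect over repeated trials with no true difference.** Let successes be Binomial(134, 0.60) and Binomial(67, 0.60), remove k S+A failures, apply the Step 3 test to complete cases, and sum over all outcomes. For k = 4, 6 and 10 the false-positive rate is about 0.07, 0.09 and 0.145 at nominal 0.04, and about 0.02, 0.03 and 0.055 at nominal 0.01.

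**Step 5. Dependence on the loss pattern.** Suppose the whole allowance is used: 18 S+A and 9 AA lost, AA at random, true rate 0.60 in both arms. If a share s of the S+A losses are failures, observed S+A CCS = [134 × 0.60 − 18(1 − s)]/116. By the normal approximation:

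| s | Observed difference | Rejection at 0.04 | Rejection at 0.01 |
|---|---|---|---|
| 40% (random) | 0 | 0.040 | 0.010 |
| 60% | 0.031 | 0.089 | 0.027 |
| 80% | 0.062 | 0.175 | 0.066 |
| 100% | 0.093 | 0.302 | 0.139 |

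Here 27/201 = 13.4% are missing, so multiple imputation would be triggered; these complete-case rates ignore it. With random loss there is no inflation.

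**The case against.** Much of the case on the other side stands.

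- **Outcomes might be thought already lost.** The documents report no such withdrawal. They permit the loss; they do not show it.
- **Selective withdrawal might be thought invisible.** It would not be. Section 10.6 records a reason for each withdrawal, and 14.7 plans tables by treatment group that include premature termination. Losses confined to one arm would show there.
- **The analysis is not blind to it.** The 14.9 grid includes the scenario with all missing S+A subjects as failures, which in Step 2 returns exactly 80/134. What remains is that the grid does not use the reason for withdrawal, leaves a small fraction of changed scenarios undefined, and cannot supply the unobserved outcome.
- **Withdrawal might be thought to erase a known SSSI.** Data collected before withdrawal are kept by default, so a recorded SSSI stays. The exposure is to KOOS Pain not yet collected and to SSSIs after exit.
- **Removal of collected data might look like a second route for the investigator.** Earlier data are "included in the study database, unless the subject requests otherwise in writing", but that request belongs to the blinded subject, and its limits depend on consent text and law. It does not support this point.
- **It might be inferred that the exit form takes no outcome.** The form is not shown. One can say only that 10.6 requires none.
- **Sections 10.6 and 10.4.8 might be read as a flat contradiction.** Section 10.6 is permissive, while 10.4.8 sets the steps before declaring loss. The fair description is an unclear boundary.
- **Re-entry is allowed.** But 10.6 offers it to subjects who chose to leave or were lost, not to those withdrawn by the investigator.
- **Enrollment has stopped.** Only remaining follow-up can benefit, but section 7.0 continues it to month 24.

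**Conclusion.** The point holds as a design weakness. Section 10.6 gives an investigator who knows the arm discretion to end outcome collection on grounds related to the endpoint, after a treatment that is already complete, while neighbouring sections keep comparable subjects in follow-up.

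The size depends on assumptions about loss that the documents neither confirm nor exclude. Losing 4 to 10 S+A failures moves observed S+A CCS by 1.8 to 4.8 points. That would not make a null data set significant by itself, but if it happened systematically it would raise the complete-case false-positive rate from 0.04 to between about 0.07 and 0.145. Random loss has no such effect, and loss of AA failures biases the other way. These figures bound a risk; they do not predict or show a bias in this trial.

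**What to change.** In 10.6:

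1. Remove missed visits and protocol non-compliance as grounds for ending follow-up, and refer to 10.4.8 for how such subjects are pursued.
2. State that a subject withdrawn by the investigator for an adverse event or other reason is still asked for KOOS Pain and reoperation/SSSI status at exit and at months 12 and 24, by ePRO or telephone, unless consent is withdrawn.
3. Keep the existing exits for subjects found not to meet criteria at surgery (14.8) and for terminated sites (16.3), so the new text does not conflict with them.

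Leave the rule on a subject's written request about collected data as it is.

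The cost is a wording amendment with IRB/REB approval where required (13.2), a check that the Study Exit Form holds the two items, and a few more contacts with poorly compliant subjects. Treatment, sample size and the planned tests are unchanged.

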11.0 Safety Management—Medical Events/Adverse Events

Adverse events that occur either intraoperatively or during the follow-up phase of the study protocol are to be recorded on an Adverse Event Form whether noted by the Investigator or the subject. Sites should report only those adverse events that are related to the implant (AccuFill), Subchondroplasty Instrumentation (AccuPort Cannulas), or study procedure (Subchondroplasty and/or Arthroscopy), or those that are considered serious. Sites should also take into consideration the possibility of a temporal relationship between a potential adverse event and the study implant, instrumentation or procedure. Any events that are pre-existing (prior to surgery) are not considered adverse events, unless a pre-existing complication or event has changed in severity or intensity during the study period.

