9.5.2 Subchondroplasty Procedure

After randomization to the study group, subjects assigned to the SCP + Arthroscopy group will undergo the Subchondroplasty portion of the procedure before or after the Arthroscopy portion per the surgeon's discretion. All operative procedures are to be performed under aseptic conditions according to the institution's standards. The same Arthroscopic procedures reported above for Arthroscopy Control subjects should be performed for Subchondroplasty + Arthroscopy subjects. The Subchondroplasty surgical technique is described in detail in Appendix B, with the required steps outlined below.

- The preoperative MRI should be used in planning the access point, trajectory and depth of the AccuPort® cannula(s) for accessing the location of the BML(s).
- AccuPorts should be placed using fluoroscopic guidance.
- Use of the SCP Navigation guide is optional.
- AccuFill should only be mixed with saline, for consistency between subjects.
- Appropriate volume of AccuFill should be used to adequately fill the area(s) of BML(s) taking care not to over-pressurize or overfill the defect. Multiple fluoroscopic images should be taken during injection to check for extravasation of material.
- Any extravasation of material into surrounding soft tissues should be

thoroughly irrigated at the time of the procedure.

- An arthroscopic examination of the joint should be performed after injection to check for any material in the joint space. Any material found should be evacuated from the joint utilizing suction and lavage.

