11.1 Event Classification

Adverse Event (AE):

An adverse event is any untoward medical occurrence, unintended disease or injury, or

untoward clinical signs (including abnormal laboratory findings) in subjects whether or not related to the investigational medical device. This definition includes events related to the AccuFill implant or Subchondroplasty Surgical Instrumentation as well as those related to the Subchondroplasty Procedure.

Serious Adverse Event (SAE):

A Serious Adverse Event is any adverse event that:

- a. led to death.
- b. led to serious deterioration in the health of the subject, that either resulted in:
 1. a life-threatening illness or injury, or
 2. a permanent impairment of a body structure or a body function, or
 3. in-patient or prolonged hospitalization, or
 4. medical or surgical intervention to prevent life-threatening illness or injury or permanent impairment to a body structure or a body function.
- c. led to fetal distress, fetal death or a congenital abnormality or birth defect.

Planned hospitalization for a pre-existing condition, *with the exception of a lower extremity surgical procedure*, or a procedure required by the protocol, without serious deterioration in health, is not considered a serious adverse event.

Adverse Device Effect (ADE):

An Adverse Device Effect is an adverse event related to the use of the AccuFill implant or SCP Surgical Instrumentation (AccuPort Delivery Cannulas). This definition includes adverse events resulting from insufficient or inadequate instructions for use, deployment implantation, installation, or operation, or any malfunction of the medical device, as well as any event resulting from use error or from intentional misuse of the medical device.

For the purposes of this study protocol, all AEs will be assessed for relationship to the AccuFill implant or SCP Surgical Instrumentation. Any AEs considered to be possibly, probably, or definitely related to the implant or SCP Surgical Instrumentation will be considered as potential ADEs in study analysis and/or reporting.

Serious Adverse Device Effect (SADE):

A Serious Adverse Device Effect is an adverse device effect that has resulted in any of the consequences characteristic of a serious adverse event.

Unanticipated Serious Adverse Device Effect (USADE)

An Unanticipated Serious Adverse Device Effect is a serious adverse device effect that is not identified in nature, severity, or degree of incidence in Appendix A. Package Insert.

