11.5 Safety Reporting

All Adverse Events and Serious Adverse Events will be reported on an Adverse Event Form to the Sponsor as soon as possible after the Investigator first learns of the event. The Investigator must report all SAEs that meet the criteria below to a Zimmer Biomet Study Representative within twenty-four (24) hours after becoming aware of the incident:

- Definitely, probably or possibly related to the Study Procedure(s) and/or Study Implant AND unexpected

The Investigator is responsible for notifying their IRB/REB of all Adverse Events, including SAEs, in accordance with local regulations and institutional policies.

If an Unanticipated Serious Adverse Device Effect (USADE) is identified by the Sponsor, it will be promptly reported to concerned Investigators and regulatory authorities as required by applicable regulatory requirements. If applicable per their reporting requirements, the Investigator or Designee will report the USADE to their IRB/REB or EC.

Device deficiencies resulting in an adverse event will be documented on the Adverse Event form. Device deficiencies that could have led to a medical occurrence but did not lead to an adverse event will be reported to the sponsor within 48 hours of becoming aware of the event. The sponsor will process the device deficiency according to local complaint reporting procedures.

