14.8 Analyses Populations

Subjects will be assigned a subject ID number after verification that they met the preliminary study criteria, have signed the informed consent form, scheduled a surgery date and Inclusion/Exclusion has been entered into the Electronic Data Capture System. A Randomization ID will be assigned just prior to the time of surgery.

The **intent-to-treat (ITT)** population is defined as subjects who complete the preoperative procedures and are randomized just prior to the time of surgery. The final determinations of inclusion and exclusion criteria and stratum assignment are made during surgery. The allowable exclusions will be any subject who does not meet inclusion or exclusion criteria based on surgeon review. Preoperative and surgical data will be collected from these subjects, along with the reason for the subject being excluded from the study. However, the subject will be exited and will not continue for follow-up. The baseline analyses and analyses of population characteristics will be performed on the ITT group.

The **modified ITT (mITT)** population is defined as subjects who meet all inclusion and exclusion criteria and have an arthroscopy with SCP or arthroscopy alone as outlined in Section 9.5. The modified ITT population will be used for the primary and secondary efficacy analyses and safety analyses.

The **per-protocol (PP)** population is all subjects who are assigned a study number, receive treatment as randomized per the study procedure and complete the study according to the protocol. Exclusions for the per-protocol analysis population include, but are not limited to, protocol violations and any actions that compromise the efficacy of the procedure. The primary variables analyses will be done on this population to determine if study findings would have differed with the inclusion of the excluded subjects.

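### The rule for which adverse events are recorded contradicts itself, and the safety set leaves out operated subjects judged ineligible

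*Combined protocol and SAP*

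**What the plan says.** **Recording of events.** Section 11.0 opens by requiring that intraoperative and follow-up AEs go on the Adverse Event Form. It then narrows this: "Sites should report only those adverse events that are related to the implant (AccuFill), Subchondroplasty Instrumentation (AccuPort Cannulas), or study procedure", the only addition being events covered by "or those that are considered serious". Section 11.1 defines an AE as covering events "whether or not related to the investigational medical device" and adds that "all AEs will be assessed for relationship to the AccuFill implant or SCP Surgical Instrumentation". Section 11.5 states: "All Adverse Events and Serious Adverse Events will be reported on an Adverse Event Form to the Sponsor as soon as possible". Sections 9.6 and 9.7.2 speak of all or any AEs but refer back to Section 11.0 for the procedure.

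**Who knows the arm.** Section 9.4 keeps the surgeon blinded only up to the operation. The subject alone stays blinded throughout.

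**Use of the data.** Item 6 of the secondary endpoints (Sections 6.3 and 14.6) is the incidence and time to resolution of complications and AEs. Section 14.7 tabulates AE rates, and the synopsis says the tabulation is by group.

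**Safety set.** Section 14.8 says: "The modified ITT population will be used for the primary and secondary efficacy analyses and safety analyses". Membership of that set requires both satisfying every eligibility criterion and having the procedure. The same section places the last eligibility decision during surgery, by surgeon review. Subjects excluded there leave the study with no follow-up, although their preoperative and surgical data are collected. Section 9.5.2 lets the Subchondroplasty step come "before or after the Arthroscopy portion per the surgeon's discretion". Sections 10.5.2 and 10.5.4 allow the sponsor to approve enrolment of subjects who miss a criterion.

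**The concern.** There are two separate weaknesses in the safety comparison.

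First, two sites following different sections would collect different events. A site following the Section 11.0 filter drops every non-serious event that it regards as unrelated. That judgement is made where the surgeon knows the treatment, and no blinded assessor of AEs is named. The blinded independent review in Section 10.4.5 concerns KOOS decline and cross-over only. A difference between arms in recorded incidence could then reflect a difference in attribution, a difference in harm, or both.

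Second, the safety set is chosen by eligibility and not by exposure. Someone on whom a study operation was begun, possibly with AccuFill already injected, can fall outside the safety tables. Safety follow-up is one of the stated reasons for continuing to 24 months after enrolment stopped (Section 7.0), so both weaknesses bear on what the trial can still deliver.

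**Working it through.** The plan states no AE rate, attribution rate or safety sample size, so there is no figure of its own to reproduce.

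**1. Is the recording rule consistent?** Take a non-serious event in the index knee, without reoperation, that the site regards as unrelated.

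- Section 11.0, first sentence: goes on the form. Second sentence: not reported.
- Section 11.1: is an AE, and is assessed for relationship.
- Section 11.2: the form offers a not-related category, which such an event could not reach under the filter.
- Section 11.5: reported to the sponsor.
- Sections 9.6 and 9.7.2: captured, but by way of Section 11.0, where the filter sits.

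Reading the text as record everything but report only some does not resolve this. Section 11.5 has all AEs reported, and Section 12.0 says that reports are what enter the study database.

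**2. Which events are exposed to the filter?** Serious events pass whatever their cause (Section 11.0). An AE leading to reoperation or revision is recorded as serious (Section 9.7.2), and every reoperation goes on an AE form (Section 10.4.3). What remains is non-serious AEs without reoperation.

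**3. How far could the recorded comparison move?** For these events let r be the true incidence and q the share judged related, with subscript T for S+A and C for arthroscopy alone. Recorded incidence = r × q, and recorded ratio = (r_T × q_T) / (r_C × q_C). If r_T = r_C, the ratio reduces to q_T / q_C. All rates below are assumptions.

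| r_T, r_C | q_T, q_C | Recorded S+A vs AA | True ratio | Recorded ratio |
|---|---|---|---|---|
| 20%, 20% | 50%, 50% | 10% vs 10% | 1.0 | 1.0 |
| 20%, 20% | 70%, 50% | 14% vs 10% | 1.0 | 1.40 |
| 20%, 20% | 50%, 70% | 10% vs 14% | 1.0 | 0.71 |
| 20%, 20% | 80%, 40% | 16% vs 8% | 1.0 | 2.0 |
| 20%, 20% | 40%, 80% | 8% vs 16% | 1.0 | 0.5 |
| 40%, 20% | 40%, 80% | 16% vs 16% | 2.0 | 1.0 |

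With equal true incidence of 40% in both arms the ratios are unchanged and the differences double: 80% vs 40% attribution gives 32% vs 16%. The last row shows that a true doubling could also be hidden.

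**4. Who falls outside the safety set?**

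- *Found ineligible during surgery.* Randomised and in the operating room, but fails the eligibility part of the mITT definition. Because the Subchondroplasty step may come first, AccuFill may already be in place. Follow-up stops, and surgical data, including the intraoperative AE field in Section 9.5.3, are kept.
- *Enrolled under a waiver.* Treated, and nothing in Section 14.8 ends follow-up, but on a literal reading not every criterion is met, so the subject is outside mITT.

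The documents give no count for either group, so no size is put on this part.

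**The case against.** The strongest reply is that little is lost.

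- The clinically weightiest events (serious events, reoperations, revisions) are captured regardless of attribution. This stands and limits the point to non-serious events without reoperation.
- The form's scale in Section 11.2 sets a low bar: an event can be possibly related even when another cause is present. Section 11.0 also asks sites to weigh timing. Many index-knee events would then qualify in either arm. This stands as a reason why attribution might be high and similar in both arms, but Section 11.0 does not say that possibly related counts as related for its filter.
- Safety is descriptive, with counts and percentages and no hypothesis test, and Section 14.7 frames it around events associated with treatment. This is true, but the tables are by arm and will be read as a comparison.

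Some stronger readings are tempting and are not supported:

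- *That the filter produces a spurious excess in S+A, because implant and cannula exist only there.* The third route, the study procedure, expressly includes arthroscopy, which every subject has. Attribution could differ either way or not at all.
- *That the filter is the settled rule.* Other sections say the opposite, and the documents do not show which one sites followed.
- *That excluded subjects supply no safety data.* Their surgical data are collected, and Section 14.7 promises listings of all events. What is missing is their place in the mITT tables and anything after exit.
- *That the subjects removed are those with complicated surgery.* Section 14.8 excludes for eligibility, not for complications, and most criteria are settled before the operation.

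**Conclusion.** The point holds in two parts. The recording rule is internally inconsistent and needs reconciling whatever sites did in practice. If the Section 11.0 filter was applied, the between-arm comparison of non-serious events without reoperation depends on attribution made where the surgeon knows the arm. Under assumed attribution shares of 40% to 80% the recorded ratio could lie anywhere from 0.5 to 2.0 when the true ratio is 1.0. Equal attribution would leave it at 1.0. The ratio over all AEs would usually move less, because serious events and reoperations are unaffected. Neither direction nor size can be determined from the documents.

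The safety set is defined by eligibility, so some operated subjects are outside the safety tables. That follows from the text alone. How many there are, and whether any had received AccuFill, is not stated. The planned 134 S+A subjects should not be used to estimate the number, because enrolment stopped early. The primary efficacy test is not at issue here.

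**What to change.** - **Sections 11.0, 11.1, 9.6 and 11.5:** state one rule. At the remaining calls, record AEs of the index knee regardless of attribution, together with all serious events as now. Keep relatedness as a field on the form and not as a condition for completing it. Make the between-arm tables on all recorded events, with related events as a subset.
- **Section 14.8:** define a safety set of all subjects in whom any study procedure was begun, analysed by procedure received, using all data collected on them. This brings in subjects excluded during surgery (with their surgical data) and those enrolled under a waiver. Say how events after a cross-over operation (Section 10.4.4) are counted.
- **Final report:** state as limitations that earlier non-serious AEs may have been filtered, that ascertainment changed part-way through follow-up, and that subjects excluded at surgery have no data after exit. Give the number of such subjects by arm.

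The cost is wording, a few more AE forms at calls that already screen for AEs, and a mixed ascertainment period. Presenting events before and after the change separately would make that period visible. Recruitment ended in November 2020, so recovering past unrecorded events or resuming follow-up of exited subjects would not be cheap, and neither is asked for. Section 10.6 requires new consent even for withdrawn or lost subjects who return.
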